4.4.4. Exploratory Immunology Endpoints

Details of the immunology endpoints will be included in a separate biomarker analysis plan.

4.4.5. Exploratory PRO Endpoints

Patient reported outcomes, the HBQOL and the EQ-5D, will be analysed using the ITT analysis set.

For HBQOL summary statistics for actual values and changes from baseline in overall score and each of the 6 domains (psychological well-being, anticipation anxiety, vitality, stigma, transmissibility and vulnerability) will be displayed by visit for Arms 1, 2, 3 and 4. HBQoL v1.0 (Spiegel BM, 2007) will be used to derive scores for HBQoL.

The EQ-5D quality of life instrument provides a utility score and thermometer score. The descriptive system comprises 5 dimensions: mobility, self-care, usual activities, pain/discomfort, and anxiety/depression with 3 levels for each dimension from level 1 = no problem to level 3 = extreme problems.

The health state is defined by combining the levels of answers from each of the 5 questions. Each health state is referred to in terms of a 5-digit code. For example, state 11111 indicates no problems on any of the 5 dimensions, while state 11223 indicates no problems walking about, no problems with self-care, some problems with performing usual activities, moderate pain or discomfort and extremely anxious or depressed.

The health state 5-digit code is translated into the utility score, which is valued up to one (representing perfect health) with lower values meaning worse state, according to the methodology described in Dolan P., 1997. The UK values set described in Dolan P., 1997 will be used for all subjects regardless of their country origin.

Summary statistics for actual values and changes from baseline in EQ-5D thermometer and utility scores will be presented by visit for Arms 1, 2, 3 and 4.

A listing of the utility score and thermometer values will be produced.

4.5. Safety Analyses

The safety analyses will be based on the Safety Analysis Set, unless otherwise specified. To allow comparison between safety in active treatment vs placebo, and loading dose vs

no loading dose, selected safety displays will be presented by study Weeks 1-12, Weeks 13-24, and Weeks 25-48; refer to the OPS for details of which outputs should be presented by Week, and refer to Section 6.2.2.2 for definitions of assessment windows for adverse events.

4.5.1. Extent of Exposure

Extent of exposure will be summarized using summary statistics. Number of subjects with < 6 weeks <= 12 weeks exposure, <= 24 weeks exposure, > 24 weeks exposure will be presented, and the overall duration of exposure (see Output and Programming Specification for deviation of overall duration of exposure) will be summarized. Study intervention compliance will be summarized as described in Section 6.1.5.Adverse Events

Number of days of exposure to study drug will be calculated based on the formula: Duration of Exposure in Days = Last injection date - First injection date + 1

The cumulative dose will be based on the formula:

Cumulative Dose = Number of Injections of 300mg x 300mg + Number of Injections of 150mg x 150mg

4.5.2. Adverse Events

An adverse event (AE) is considered treatment emergent if the AE onset date is on or after treatment start date. If AE start date is completely missing and the end date is on or after the treatment start date, the AE will be assumed to be treatment emergent. All AE summaries will be based on treatment emergent events unless otherwise specified.

Adverse events will be coded using the latest version of MedDRA coding dictionary, to give a preferred term and a system organ class. These preferred terms and system organ classes will be used when summarising the data. The severity of AEs and SAEs will be determined by the investigator according to the DAIDS grading system Version 2.1 [National Institute of Allergy and Infectious Diseases. Division of AIDS, 2017], unless specified otherwise in the protocol.

For AEs by maximum grade summary tables, if a participant reports an AE more than once within an SOC/PT, the AE with the most severe intensity will be included in summaries. Relationship to study treatment, as indicated by the investigator, is classified as "not related" or "related". Adverse events with a missing relationship to study treatment will be regarded as "related" to study treatment.

The following table AE summaries will be presented:

- 1. AEs overview: summarize the number and percentage of participants with any adverse event, AEs related to study treatment, AEs leading to permanent discontinuation of study treatment, withdrawal from the study, any serious adverse events (SAE), SAEs related to study treatment, fatal SAEs and fatal SAEs related to study treatment.
- 2. All AEs by system organ class (SOC) and preferred term (PT)

- 3. All AEs by SOC and PT and maximum grade
- 4. All drug-related AEs by SOC and PT
- 5. All drug-related AEs by SOC and PT and maximum grade
- 6. Serious AEs (SAEs) by SOC and PT
- 7. AEs leading to withdrawal from the study by SOC and PT
- 8. AEs leading to permanent discontinuation of investigational product by SOC and PT
- 9. AEs leading to withdrawal from the study by SOC and PT and maximum grade
- 10. AEs leading to permanent discontinuation of investigational product by SOC and PT and maximum grade
- 11. Fatal AEs by SOC and PT
- 12. AEs by overall frequency
- 13. Serious, Non-serious and Drug-Related AEs by SOC and PT (number of subjects and occurrences). This will be presented for Overall, and for Week 1 12, Week 13 24, and Week 25 Week 48.
- 14. Serious Fatal and Non-Fatal Drug-Related AEs by Overall Frequency

Number of participants with AEs will be summarized if it is not specified otherwise.

In summary tables where AEs are presented by SOC, PT, and maximum grade, SOCs will be sorted in descending order of the total incidence then alphabetically, PTs will be sorted in descending order of the total incidence then alphabetically within the SOC.

For completely missing or partial missing AE start date or end date, imputation rules will be applied following the rules stated in the Output and Programming Specification.

Deaths will be listed including primary cause of death.

4.5.2.1. Adverse Events of Special Interest

The following AEs of special interest will be reported:

- ALT increase
- Vascular inflammation and complement activation
- Thrombocytopenia
- Renal injury
- Injection site reactions

An up to date list of specific MedDRA Queries (SMQs), high level terms (HLTs) or individual preferred terms (PTs) used to identify AESIs is periodically updated and stored in a central location. At the time of DBR, the latest version of the terms will be extracted and used to identify AESIs.

All AEs of special interest will be summarized by SOC and PT, and also summarized by SOC, PT and maximum grade. Serious AESIs will be summarized by SOC and PT. All AEs of special interest will be listed.

Separate outputs will be created for each AESI category (ALT increase, vascular inflammation and complement activation, thrombocytopenia, renal injury and injection site reactions) to explore the data in more detail if data permits.

Event Characteristics: The characteristics of all event occurrences during the post-baseline period will be summarized, which looks at event characteristics (serious, drug-related, leading to withdrawal, severe or Grade 3-4, fatal), number of events per participant, outcome, maximum grade or intensity and action taken.

4.5.2.2. COVID-19 Assessment and COVID-19 AEs

A standardized MedDRA Query (SMQ) will be used to identify all COVID-19 AEs.

The overall incidence of AEs and SAEs of COVID-19, COVID-19 AEs leading to study intervention discontinuation, COVID-19 AEs leading to study withdrawal, and Grade 3 and 4 COVID-19 AEs / severe COVID-19 AEs will be summarized. The incidence of these events at individual PT level can be obtained from the standard AE/SAE summaries.

COVID-19 assessments for participants with potential, suspected or confirmed COVID-19 AEs will be summarized.

If >5% participants overall report ≥1 COVID-19 AE, then onset and duration of the first occurrence of COVID-19 AEs, and COVID-19 AE symptoms (from the COVID-19 eCRF page) will be summarized. The same rule will apply to COVID-19 SAEs.

4.5.3. Additional Safety Assessments

4.5.3.1. Laboratory Data

Only central lab data will be used for summary analyses and figures; local lab data will be included in listings, as appropriate.

Summary statistics for changes from baseline for each numeric parameter at each visit will be presented, separately for all clinical chemistry parameters, all hematology parameters and all urinalysis parameters.

For immunology parameters, summary statistics for actual value and change from baseline data for each parameter at each visit will be presented, separately for all numeric parameters. Listings will also be created.

Ang-II will be included in the immunology summaries and listings and additionally a listing of all Ang-II lab values will be presented. Plots showing mean actual and change from baseline values of Ang-II over time will be presented.

For categorical immunology parameters c-ANCA and p-ANCA, summary table of baseline Negative to post-baseline Positive, baseline value no change, and baseline Positive to post-baseline Negative will be created. Listing will be created as well.

For coagulation parameters Prothrombin Intl. Normalized Ratio (INR), Prothrombin Time (PT) and Activated Partial Thromboplastin Time (aPTT), summary statistics for actual at each visit will be presented. Listing will be created as well.

Shift tables for laboratory parameters showing baseline toxicity versus maximum post-baseline (on-treatment and off-treatment periods combined) toxicity for each grade (Grade1, Grade 2, etc.) for chemistry and hematology parameters will be provided.

Increase to Grade 3 or higher lab abnormalities for platelets, ALT, AST, INR, total bilirubin, serum creatinine, eGFR, ACR will be summarized.

Laboratory values outside of normal range will be summarized and listed.

Grading categories for laboratory tests are determined using the DAIDS grading system Version 2.1 [National Institute of Allergy and Infectious Diseases. Division of AIDS, July 2017].

Summary of post-baseline hepatobiliary laboratory abnormalities will be provided.

Liver monitoring and stopping event reporting will be summarized and listed. The Liver monitoring and stopping criteria are described in the protocol Section 7.1.1.

The worst-case urinalysis results post-baseline (on-treatment and off-treatment periods combined) relative to baseline will be summarized.

Potential Drug induced vascular injury and complement monitoring/stopping event will be summarized and listed based on laboratory parameters (C3, C4, Bb, C5a, hs-CRP, MCP-1, p-ANCA, c-ANCA, eGFR, Bilirubin, and platelet count). The Drug Induced Vascular Injury and Complement monitoring and hold or stopping criteria are described in the protocol Section 7.1.2.

Haematological monitoring/stopping event will be summarized and listed based on laboratory parameters (platelet count and anti-platelet antibodies). The haematological monitoring and stopping criteria are described in the protocol Section 7.1.3.

Potential Drug induced kidney injury (renal) monitoring and hold or stopping events will be identified programmatically and will be summarized and listed based on laboratory parameters (ACR, Urinalysis RBC, serum creatinine, and eGFR). The kidney injury monitoring and stopping criteria are described in the protocol Section 7.1.4.

Hold/stopping event profile will be provided for any subject who has met hold or stopping criteria specified in protocol Section 7.1. Relevant information will be reported, including baseline characteristics, AEs/SAEs, concomitant medication, medical history/current medical conditions, study treatment administration details, laboratory values, and individual line plots of complement (C3/C4/C5a/Bb), inflammatory markers (hs-CRP/MCP-1), serum creatinine/creatinine clearance or eGFR/ACR, and platelet count.

TMF-13936631 **CONFIDENTIAL** 209668

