4.1.2. Baseline Definition

For all endpoints (except as noted in baseline definitions) the baseline value will be the latest pre-dose (GSK or placebo) assessment with a non-missing value, including those from unscheduled visits. If time is not collected or time of assessment equals that of the first dose, Day 1 assessments are assumed to be taken prior to first dose and used as baseline. If there are multiple assessments collected at the same scheduled time, the average of these assessments will be used as the baseline.

Unless otherwise stated, if baseline data is missing no derivation will be performed and baseline will be set to missing.

Baseline of eGFR and serum creatinine is defined as the mean of all pre-dose values, from screening to Day 1 pre-dose assessment.

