6.2.2.1. Definitions of Assessment Windows for Early Termination Visits

Laboratory and vital signs data collected at Early Termination Visits will be assigned to assessment windows, according to the actual date.

Analysis	Parameter	Target	Analysi	s Window	Analysis
Set / Domain	(if applicable)		Beginning Timepoint	Ending Timepoint	Timepoint
Lab, Vital	Numeric				
Signs	parameters	1	1	2	Week 1 Day 1
		4	3	6	Week 1 Day 4
		8	7	9	Week 2 Day 8
		11	10	12	Week 2 Day 11
		15	13	18	Week 3
		22	19	25	Week 4
		1+7(x-1)	1+7(x-1)-3	1+7(x-1)+3	Week x
		169	166	172	OT-Week 1
		176	173	179	OT-Week 2
		190	180	203	OT-Week 4
		218	204	231	OT-Week 8
		246	232	259	OT-Week 12
		274	260	287	OT-Week 16

302	288	315	OT-Week 20
330	316	340	OT-Week 24

Notes:

- 1. Week x includes on-treatment weeks 5-24
- 2. Visit windows are to be used for windowing of Early Termination visits only

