6.2.2.2. Definitions of Assessment Windows for Adverse Events

To allow comparison between safety in active treatment vs placebo, and loading dose vs no loading dose, selected safety displays will be presented by study Weeks 1-12, Weeks 13-24, and Weeks 25-48. Adverse events are not associated with a specific visit therefore the study week they are assigned to will be based on the AE start date.

Analysis	Parameter	Analysis Window		Analysis	
Set / Domain	(if applicable)	Beginning Timepoint	Ending Timepoint	Timepoint	
Adverse	All				
Events		1	81	Weeks 1 – 12	
		82	165	Weeks 13 – 24	
		166	-	Weeks 25 – 48	

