6.2.3. Study Period

Assessments and events will be classified according to the time of occurrence relative to the study intervention period. Off Treatment Day 1 occurs 7 days after the last study treatment dose received, regardless of whether the participant completes treatment as planned or the participant is withdrawn from study treatment.

Study Intervention Period	Definition
Pre-Treatment	Date ≤ Study Treatment Start Date
On-Treatment	Study Treatment Start Date < Date ≤ Off Treatment Day 1 – 1 day
Post-Treatment	Date ≥ Off Treatment Day 1

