6.2.5. Multiple measurements at One Analysis Time Point

Multiple Measurements at One Analysis Time Point

- Handling of multiple measurements within an analysis window for primary endpoint is described in Section 4.2.2
- Assessments on unscheduled visit will not be included in the tables of summary statistics by visit but
 will be included in the associated listings. Also, such assessments on unscheduled visit will be used
 for the "any time on-treatment" or "Any visit post-baseline" time point.
- If there are multiple assessments on scheduled visit within visit window, will query the site to identify the valid assessment as the assessment for the scheduled visit.
- Participants having both High and Low values for Normal Ranges at any post-baseline visit for safety parameters will be counted in both the High and Low categories of "Any visit post-baseline" row of related summary tables.

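### The laboratory grade-shift tables and the worst-case urinalysis summary pool active, placebo and follow-up values in Arms 3 and 4; the SAP should also show both by study period

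*SAP*

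**What the plan says.** SAP 4.5.3.1 defines two laboratory displays as a single worst value per participant. For chemistry and haematology it plans "Shift tables for laboratory parameters showing baseline toxicity versus maximum post-baseline (on-treatment and off-treatment periods combined) toxicity for each grade". For urinalysis: "The worst-case urinalysis results post-baseline (on-treatment and off-treatment periods combined) relative to baseline will be summarized".

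SAP 4.5 says that selected safety displays will be split into Weeks 1-12, 13-24 and 25-48, so that active treatment can be compared with placebo and loading with no loading. It leaves the choice of displays to the OPS. On timing it tells the reader to "refer to Section 6.2.2.2 for definitions of assessment windows for adverse events". Section 6.2.2.2 sets those windows at Days 1-81, 82-165 and 166 onward. It explains that adverse events have no visit attached, so "the study week they are assigned to will be based on the AE start date". The one display that the SAP itself names as split by period is adverse event table 13 in SAP 4.5.2.

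Three other rules bear on the point:

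- The laboratory windows in SAP 6.2.2.1 have a narrow use: "Visit windows are to be used for windowing of Early Termination visits only".
- SAP 6.2.5 limits the by-visit tables: "Assessments on unscheduled visit will not be included in the tables of summary statistics by visit". Unscheduled values do count in summaries over any post-baseline visit.
- SAP 6.2.3 ends the on-treatment period by reference to study treatment, whether active or placebo: "Off Treatment Day 1 occurs 7 days after the last study treatment dose received".

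Protocol 9.4.5 asks for maximum post-baseline toxicity grade by arm and mentions no period split.

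**The concern.** In Arms 1 and 2 the combined maximum describes 24 weeks of active drug plus follow-up. In Arms 3 and 4 it describes something else. A Grade 3 value in Arm 4 may have arisen on placebo, on active drug or in follow-up, and the table does not say which. Splitting only into on- and off-treatment would not help, because placebo dosing counts as on-treatment.

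Timing matters for this drug. Protocol 4.2.1 reports that 33% of treatment-naive participants in the earlier study had ALT at or above 3x ULN, and Protocol 6.5.3 warns of ALT flares after stopping. A reader of the pooled tables cannot separate on-drug elevations from post-treatment flares, nor compare either with the concurrent placebo weeks in Arm 4. What is at stake is how the safety tables can be read. The primary endpoint and regimen selection do not depend on them.

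**Working it through.** The plan gives no figure of its own on this point. The check counts the samples that feed the maximum and then asks what the pooled maximum can show.

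**1. Scheduled samples.** Inputs are the post-baseline visits with chemistry, haematology and urinalysis in Protocol Tables 2 to 4.

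- Days 8, 15, 22, 29, 36, 43, 50: 7 visits.
- Days 57 to 162, weekly: 16 visits.
- Off-treatment Days 169, 176, 190, 218, 246, 274, 302, 330: 8 visits.
- Total: 7 + 16 + 8 = 31.

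**2. Split by period.** Applying the adverse event limits unchanged gives 11/12/8. Those limits put Day 85 in Weeks 13-24. If Day 85 is drawn before dosing, in Arm 4 it still reflects placebo alone. In the same way, Day 169 comes 7 days after the last dose on Day 162 and reflects the second dosing period. Attributing each sample to the doses before it gives Days 8-85 = 12, Days 92-169 = 12, and Day 176 onward = 7.

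| Arm | First period | Second period | Later follow-up |
|---|---|---|---|
| 1 and 2 | 12 active | 12 active (150 mg in Arm 2) | 7 |
| 3 | 12 active | 12 placebo after active | 7 |
| 4 | 12 placebo | 12 active | 7 |

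As shares of 31: 12/31 = 39%, 12/31 = 39%, 7/31 = 23%. In Arm 4, 39% of the scheduled samples precede any active drug. In Arm 3, 19 of 31 (61%) come after the active phase.

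Drawing Day 85 before dosing is an assumption for chemistry and urinalysis; among the safety laboratory tests, the schedule says so only for the local platelet count. It matches the convention in SAP 4.1.2 when no time is recorded: "Day 1 assessments are assumed to be taken prior to first dose and used as baseline".

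**3. What the pooled maximum can show.** As an illustration, assume independent periods, no carry-over, and a per-period risk of 5% off drug and 10% on drug. The formula is P(any) = 1 - (1 - p1)(1 - p2)(1 - p3).

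- Arm 3: 1 - 0.90 x 0.95 x 0.95 = 18.8%.
- Arm 4: 1 - 0.95 x 0.90 x 0.95 = 18.8%.
- Arm 1: 1 - 0.90 x 0.90 x 0.95 = 23.1%.
- A Weeks 1-12 table would show 10% in Arms 1-3 against 5% in Arm 4.
- Share of flagged Arm 4 participants with an event in the placebo weeks: 5% / 18.8% = 27%.

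Over off-drug risks of 2% to 10% and risk ratios of 2 to 3, Arms 3 and 4 are always equal (7.8% to 43.3%), and the placebo share runs from 21% to 28%. These risks are assumed, not taken from the documents.

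**4. Precision of the split.** In Weeks 1-12, each population has about 3 x 66 = 198 participants on active drug and 22 on placebo. With no events, the upper limits of the exact two-sided 95% intervals are 1 - 0.025^(1/22) = 15.4% and 1 - 0.025^(1/198) = 1.8%.

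**The case against.** The case on the other side is substantial.

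- **No contradiction.** SAP 4.5 promises a split for selected displays only and does not say that these two are among them. The combined tables do what Protocol 9.4.5 asks. This stands. A reader might infer that the SAP contradicts itself, or that split tables will not be produced. The documents support neither, because the selection sits in the OPS.
- **No window needed for scheduled samples.** A reader might also infer that the split cannot be done because the only period windows are for adverse events. SAP 6.2.2.2 gives the reason for those windows: adverse events have no visit. Scheduled laboratory samples carry a visit label and can be grouped by it. Only unscheduled samples and the boundary visits need a rule.
- **Other outputs cover part of the ground.** Adverse event table 13 is split by period, so laboratory abnormalities reported as adverse events already appear that way, though without grade. Numeric laboratory changes and immunology biomarkers are shown by visit. The biomarkers are the main comparator role that Protocol 4.2.2 gives Arm 4. Hold/stopping profiles set laboratory values beside dosing details.
- **Scope.** The Grade 3-or-higher, hepatobiliary and vital-sign summaries also state no split. That is true, but they are not expressly defined over combined periods.

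What remains is narrow. By-visit tables give change from baseline rather than worst grade, and they leave out unscheduled samples, such as those from the twice-weekly liver monitoring in Protocol 7.1.1. No output named in the SAP gives worst laboratory grade for Arm 4's placebo weeks.

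**Conclusion.** The point holds as a cheap improvement to descriptive safety reporting. As worded in SAP 4.5.3.1, the two displays pool active, placebo and follow-up values in Arms 3 and 4, and cannot serve the active-versus-placebo aim of SAP 4.5. In Arm 4, 39% of the scheduled samples behind the maximum precede any active drug, assuming that Day 85 is drawn before dosing.

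The gain is limited. The one clean contrast is Arms 1-3 against Arm 4 in Weeks 1-12, and Protocol 4.2.2 says that Arm 4 comparisons are not powered. Arm 3 in Weeks 13-24 is not a clean placebo period, because Protocol 4.3 gives a half-life of about 3 weeks. If the OPS already splits these tables, the point reduces to stating the split and the boundary rule in the SAP.

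**What to change.** Keep the combined tables. Add to SAP 4.5.3.1 that the grade-shift tables and the worst-case urinalysis summary will also be presented by Weeks 1-12, 13-24 and 25-48. State these rules with it:

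1. Assign scheduled samples by nominal visit and unscheduled samples by date. In participants who stop early, off-treatment visits run from the actual last dose (notes to Protocol Table 4), so assign those by date too.
2. In every arm, a sample drawn before the first dose of a new period belongs to the preceding period. This covers Day 85. Day 169, 7 days after the last dose, is handled the same way, giving 12/12/7. Say that this applies to these displays only, since SAP 6.2.3 counts Day 169 as post-treatment. Using one rule for all arms keeps the chance of recording a maximum equal within each period. It also keeps it equal for loading versus no loading (Arm 3 first period against Arm 4 second period).
3. Label Arm 3 in Weeks 13-24 as post-active placebo.

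The cost is a few lines of SAP text and repeat runs of existing table programs, with no new data or visits. The downside is more output and small Arm 4 cells of about 22 per population. Study-week periods also do not follow actual exposure in participants who stop treatment early.

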7.1.2. Drug Induced Vascular Injury and Complement Stopping Criteria

If any of the following are observed, results should be confirmed with a repeat sample collection and analysis, and if confirmed, further evaluation for alternative causes should be pursued in consultation with the Medical Monitor.

Repeat sample collection of C3, C4, Bb, C5a would be triggered by changes in the clinical signs and symptoms of complement activation (≥2+ haematuria; increasing urine ACR; vasculitic or purpuric rash; peripheral neuropathy; jaundice). Additional complement analyses for example CH50, Factor B level, Factor H level, sC5b-9 should also be considered in discussion with the Medical Monitor and Safety Panels.

1. Persisting & deteriorating longitudinal trends in change from baseline for C3 and/or C4 defined as:

- a. If participant's baseline C3 and/or C4 is *within* the lab's normal range at baseline: there is a sequential decline in C3 and/or C4 once levels have fallen below LLN for ≥4 weeks OR
- b. If participant's baseline C3 and/or C4 is *below* the lab's LLN at baseline: there is further sequential decline in C3 and/or C4 for ≥4 weeks OR
- c. Regardless of baseline C3 and/or C4 level: there is a ≥80% reduction in the participant's C3 and/or C4 level at any point

AND

- d. There is an associated ≥3-fold increase in Bb and/or C5a from participant's baseline OR
- e. There are associated biochemical sequelae for example, a rising high sensitivity C-reactive protein (hs-CRP); rising monocyte chemoattractant protein-1 (MCP-1); new thrombocytopenia, new renal impairment with no other explanation such as intercurrent infection OR
- f. There are associated clinical sequelae, for example, ≥2+ haematuria; increasing urine ACR; vasculitic or purpuric rash; peripheral neuropathy; jaundice OR
- g. There is new cANCA or pANCA positivity

2. Persisting & deteriorating longitudinal trends in change from baseline for Bb and/or C5a where

- a. There is a \geq 3-fold increase in Bb and/or C5a over baseline AND
- b. This is persisting or increasing week on week in sequential data plots OR
- c. There are associated biochemical sequelae for example, a rising hsCRP; rising MCP-1, new thrombocytopenia, new renal impairment with no other explanation such as intercurrent infection OR
- d. There are associated clinical sequelae, for example, ≥2+ haematuria; increasing urine ACR, vasculitic or purpuric rash; peripheral neuropathy; jaundice or any combination of these OR

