- e. There is new cANCA or pANCA positivity

Treatment Hold/Treatment Discontinuation

- Hold study treatment during evaluation of alternative causes for decreased C3 and/or C4 associated with increased inflammatory markers including one or more of hs-CRP, MCP-1, Bb and C5a
- Discontinue study treatment permanently if persistent change from baseline (≥4 weeks) in biomarker pattern (decreased C3/C4 associated with increased inflammatory markers including one or more of hsCRP, MCP-1, Bb, C5a) without clear alternative explanation.
- Discontinue study treatment permanently if suspect clinical sequelae of complement activation, drug induced vascular injury, vasculitis or auto-immunity regardless of biomarkers changes or persistence.

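### The SAP's vascular injury/complement event table omits urine blood and urine ACR, so participants who meet Protocol 7.1.2 criterion 1f or 2d only through those signs would be missed in it

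*SAP*

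**What the plan says.** SAP 4.5.3.1 (Laboratory Data) plans a summary and listing of potential drug-induced vascular injury and complement monitoring/stopping events, "based on laboratory parameters (C3, C4, Bb, C5a, hs-CRP, MCP-1, p-ANCA, c-ANCA, eGFR, Bilirubin, and platelet count". It then gives the source of the rules: "The Drug Induced Vascular Injury and Complement monitoring and hold or stopping criteria are described in the protocol Section 7.1.2".

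Protocol 7.1.2 has two criteria, each with two limbs. The first limb is the complement trigger: a defined fall in C3 and/or C4 (criterion 1) or a ≥3-fold rise in Bb and/or C5a (criterion 2). The second limb can be completed in several ways. Criterion 1f reads "There are associated clinical sequelae, for example, ≥2+ haematuria; increasing urine ACR; vasculitic or purpuric rash; peripheral neuropathy; jaundice OR". Criterion 2d repeats the same signs, including "increasing urine ACR, vasculitic or purpuric rash; peripheral neuropathy; jaundice or any combination of these OR". The introduction to 7.1.2 names them as well, as prompts for repeat complement sampling: "≥2+ haematuria; increasing urine ACR; vasculitic or purpuric rash; peripheral neuropathy; jaundice".

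Meeting criterion 1 or 2 leads first to confirmation and work-up: "results should be confirmed with a repeat sample collection and analysis, and if confirmed, further evaluation for alternative causes should be pursued". Three hold or discontinuation rules follow:

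- The hold rule concerns "decreased C3 and/or C4 associated with increased inflammatory markers including one or more of hs-CRP, MCP-1, Bb and C5a".
- Permanent discontinuation for a persistent pattern uses the same biomarkers.
- The third rule does not depend on biomarkers: "Discontinue study treatment permanently if suspect clinical sequelae of complement activation, drug induced vascular injury, vasculitis or auto-immunity regardless of biomarkers changes or persistence".

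**The concern.** The table is meant to show how often the Protocol 7.1.2 criteria were met, including the monitoring level. Its parameter list should therefore be able to detect every limb that rests on a laboratory value. Two such limbs, blood in the urine and a rising urine ACR, have no counterpart on the list, although both are measured throughout the study.

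Vascular inflammation with complement activation is an adverse event of special interest. Protocol 4.2.2 makes the placebo-first arm the comparator for these exploratory biomarker analyses. If a complement change accompanied by a urine sign is not counted, the table does not describe the protocol's own criteria, and a reader would have no way of knowing that.

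**Working it through.** There is no stated figure to reproduce. The check sets each second-limb sign in Protocol 7.1.2 against the SAP list. I read the criteria as trigger AND (any second-limb sign).

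| Second-limb sign | Criterion | On the SAP list |
|---|---|---|
| ≥3-fold Bb and/or C5a rise | 1d | Bb, C5a |
| Week-on-week persistence or increase of Bb/C5a | 2b | Bb, C5a |
| Rising hs-CRP | 1e, 2c | hs-CRP |
| Rising MCP-1 | 1e, 2c | MCP-1 |
| New thrombocytopenia | 1e, 2c | platelet count |
| New renal impairment | 1e, 2c | eGFR |
| Jaundice | 1f, 2d | bilirubin, as a stand-in |
| New c-ANCA or p-ANCA positivity | 1g, 2e | c-ANCA, p-ANCA |
| ≥2+ haematuria | 1f, 2d | none |
| Increasing urine ACR | 1f, 2d | none |
| Vasculitic or purpuric rash | 1f, 2d | none (not a laboratory value) |
| Peripheral neuropathy | 1f, 2d | none (not a laboratory value) |

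Each criterion therefore has 11 named signs: 7 visible to the list, 2 omitted urine signs and 2 purely clinical signs. The protocol offers the sequelae as examples, so the set is not exhaustive.

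**Patterns, given that the trigger is met** (the same for each criterion):

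- Patterns with at least one sign: 2^11 − 1 = 2,047.
- Patterns with none of the 7 listed signs, which the SAP list cannot see: 2^4 − 1 = 15.
- Of those, rash and/or neuropathy only: 2^2 − 1 = 3.
- Recovered by adding urine blood and urine ACR: 15 − 3 = 12.

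The patterns are not equally likely, so 15/2,047 is not an event rate.

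**Was the omission a deliberate scope?** The list includes bilirubin, which appears nowhere in the biochemical limbs 1e and 2c; its evident counterpart is jaundice in 1f and 2d. So the SAP appears to map one clinical sign to a laboratory parameter and leaves the two urine signs unmapped, without giving a reason.

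**Are the data there?** From the global schedule of activities, per completing participant after screening:

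- Complement panel: 4 + 8 + 7 = 19 visits.
- Urinalysis: 8 + 16 + 8 = 32 visits.
- Urine ACR: 4 + 8 + 8 = 20 visits.

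Each count includes Day 1, which is baseline, so the complement trigger can be seen at 19 − 1 = 18 scheduled post-baseline visits. Urinalysis and ACR are scheduled at every one of them. The next SAP output but one, for renal events, already uses ACR and urinalysis RBC.

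**Coverage of the hold and discontinuation rules.** The hold rule and the persistent-pattern rule use C3, C4, hs-CRP, MCP-1, Bb and C5a, all on the list. The clinical-suspicion rule cannot be derived from any laboratory list.

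**The case against.** The case for leaving the SAP alone has four parts.

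1. **The gap is narrow.** hs-CRP and MCP-1 need only be rising, with no threshold, and are drawn at the same visits as C3 and C4. Many participants with a urine sign would also show a listed change and be counted. This stands and limits the size of the problem.

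2. **The table is modest in scope.** It sits under Laboratory Data and is labelled as potential events. That is a fair reason for it not to capture rash, neuropathy or investigator suspicion. It does not explain the absence of two laboratory measurements from a table that covers monitoring as well as stopping events.

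3. **The information appears elsewhere.** The SAP has renal event, worst-case urinalysis, Grade 3 or higher ACR, special-interest AE and AE-discontinuation outputs, and a profile for anyone who met a Section 7.1 hold or stopping criterion. So it would be wrong to infer that the renal signs are lost from the report. But the renal criteria in Protocol 7.1.4 differ (persistent ACR ≥30 mg/g; ≥5 RBC per high-power field on microscopy), so an ACR rise that stays below 30 mg/g could meet 7.1.2 and not 7.1.4. None of the renal or laboratory summaries ties the urine sign to a complement change. The AE tables need a reported event. The SAP does not say how a participant meeting 1f or 2d only through a urine sign would be identified for the profile.

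4. **A rising ACR is non-specific.** Protocol 8.3.7.4 itself gives a tubular explanation for increased urine protein. This stands, and it bears on how the parameter is programmed. It also means the documents do not support calling these signs the most specific presentations of vascular injury.

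**Conclusion.** The omission is clear on the face of the two documents, and its consequence is limited. A participant is missed in this table only if the complement trigger is met, haematuria and/or a rising ACR is present, and no listed second-limb change is present. The documents give no rates, so the number affected cannot be derived; it may be small.

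A reader might go further and infer that qualifying events in general go uncounted, or that the report will understate how often treatment should have been held or stopped. The documents do not support that. Any listed change still captures the participant, criteria 1 and 2 lead first to confirmation and evaluation, and the biomarker hold and discontinuation rules are fully covered. The clinical-suspicion rule lies outside any laboratory table; discontinuations under it have other routes into the report through the AE-discontinuation and special-interest outputs.

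The conclusion assumes that the SAP list is closed as written, that bilirubin and eGFR stand in for jaundice and renal impairment, and that each second-limb sign suffices alone once the trigger is met.

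**What to change.** In SAP 4.5.3.1:

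- Add dipstick urine blood at the grade Protocol 7.1.2 already uses (≥2+), and urine ACR increase from baseline, to the parameter list.
- State a programming definition of *increasing* for ACR. This is a reporting definition only and leaves the protocol's clinical criteria as they are. Fix it before unblinding. Protocol 9.5 has specified sponsor staff unblinded at the third interim, and the SAP version history shows analyses requested at that interim, so staff who are still blinded should set it, with the date recorded.
- Label the table as covering only the laboratory-derivable part of Protocol 7.1.2.
- Cross-reference the existing special-interest AE, AE-discontinuation and hold/stopping profile outputs for rash, neuropathy and discontinuation on clinical suspicion.

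The cost is SAP wording and a little more programming on data already collected. Event counts may rise, and some of the added events may be non-specific ACR fluctuation; showing which sign completed each event would let the reader judge that.
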